6.2 Definition of Analysis Population

All subjects receiving at least one study product will be used for safety analyses. All subjects with at least 1 FMD measurements will be part of the intention-to-treat population. All subjects with no major deviation from the protocol will form the per-protocol population. All FMD measurements with acceptable quality will be used for analyses. Decision on the per-protocol population and FMD measurement quality will be made during blind review and documented.

6.3 Statistical Methods

FMD measurements will be taken as follows:

- Measurement 1: Baseline measurement on Day 0 (Visit 0 - Screening / Baseline / Randomization Visit)
- Measurement 2: second measurement on Week 4 (Visit 1)

- Measurement 3: third measurement on Week 8 (Visit 2 – End of Study Visit)

In order to evaluate a potential effect size among groups according to Primary and Secondary Endpoints the comparison will be made comparing:

- Measurement 3 vs Measurement 1
- Measurement 2 vs Measurement 1
- Measurement 3 vs Measurement 2

Parametric or non-parametric tests, ANOVA and Kruskal-Wallis tests, will be performed basing on the normality of the data.

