Several pathophysiological states are characterized by a variable degree of endothelial dysfunction, mainly due to a decrease in endothelium-dependent vasodilation. A comprehensive but not exhaustive list of these conditions includes hypercholesterolemia, atherosclerosis, diabetes mellitus and heart failure. Specifically, an impairment in flow mediated endothelium-dependent vascular dilation was observed in hypercholesterolemia. This may be due to increased levels of intracellular superoxide inactivating NO more rapidly (Loffredo, 2012).

Since NO bioavailability is reduced in the presence of reactive oxygen species (ROS), with subsequent production of other compounds including peroxynitrite, quantification of NO and peroxynitrite levels is currently proposed as a marker of oxidative stress.

In order to monitor the beneficial antioxidant effects of ubiquinol in this respect we will evaluate

- 1) Plasma levels of nitric oxide quantified in terms of its stable reaction product (nitrites and nitrates) through the Griess reaction (Tsikas 2007)
- 2) Oxidative inactivation of NO to peroxynitrite using fluorescent probes (Rios 2016).
- 3) Susceptibility to oxidation of plasma lipoprotein quantified as kinetic of conjugate

dienes formation following copper exposure (Mazzanti 2015)

2. Study Objectives and Endpoints

To evaluate the impact of a supplementation with ubiquinol (reduced form of ubiquinone or reduced CoQ10) on endothelial function and oxidative stress.

Primary Endpoint

Change in endothelium-dependent vasodilation (by means of the flow mediated dilation - FMD - technique) at week 8; comparison between both treatment groups and placebo.

Secondary Endpoints

- Change in endothelium-dependent vasodilation (by means of the flow mediated dilation - FMD - technique) at week 4; comparison between both treatment groups and placebo.
- Change in red / ox CoQ10 levels at week 4 and 8; comparison both between treatment groups and placebo
- Evaluation of plasma levels of nitric oxide quantified in terms of its stable reaction product (nitrites and nitrates) through the Griess reaction (Tsikas 2007) at week 4 and 8; comparison both between treatment groups and placebo
- Evaluation of plasma levels of peroxynitrite (evaluation of oxidative inactivation of NO to peroxynitrite using fluorescent probes (Rios 2016)) at week 4 and 8; comparison both between treatment groups and placebo.

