3.3.2 Inclusion Criteria

- Male aged 35 - 65 years (35 and 65 included).
- Post-menopausal female (without a period for more than 1 year), until 65 years (65 included).
- Subjects enrolled for primary prevention but never treated (only life style modification suggested, according guidelines).
- FMD level measured between:
2,5% < FMD baseline value < 6% (at Screening Visit).
- BMI: 18.5 - 29.9 kg/m².
- LDL Cholesterol levels between 130 and 200 mg/dl (based on previous evaluation, performed within 1 month from the Screening Visit).

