6.1 Sample Size Calculation

Sample size calculation is carried out with use of G*power Software.

The parameters used to compute sample size for this study were taken from the reference article by Gao et al 2012, a meta-analysis of 5 randomized controlled trials.

Mean and SD taken from the article by Watts GF et al 2002, one of the RCT mentioned in reference article (see fig. 2 in the article by Gao et al), were considered as appropriate values to be taken into account: considering group one mean and SD as 1.6 (1.16) and second group mean and SD as -0.4 (2.24), with 80% power and 5% two-sided significance level, 14 subjects are required for one group.

In this study, considering a 20% dropout rate, a total of 52.5 subjects should have been enrolled; a sample size equal to 51 subjects was deemed as appropriate.

It is to be noted that in this study the minimum increment of FMD reached with the number of patients provided for each group is to be considered as equal to 1.6% (according to Figure 2 shown in Gao et al, in particular by referring to the study of Watts, which provides a sample size similar to ours).

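### Section 6.3 lets a normality check pick the primary FMD test, uses baseline FMD only by subtraction, and names no method robust to the unequal variances that the planning SDs make plausible

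*Protocol*

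**What the plan says.** Section 2 defines the primary endpoint as "Change in endothelium-dependent vasodilation (by means of the flow mediated dilation - FMD - technique) at week 8; comparison between both treatment groups and placebo". Section 6.3 turns this into three contrasts between measurements, introduced by "In order to evaluate a potential effect size among groups according to Primary and Secondary Endpoints the comparison will be made comparing", the first being "Measurement 3 vs Measurement 1", and then names the tests: "Parametric or non-parametric tests, ANOVA and Kruskal-Wallis tests, will be performed basing on the normality of the data". It names no covariate and no method for unequal variances, and it does not say which of the two tests is primary.

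Baseline FMD is measured in every subject on day 0 and is also an entry criterion: "2,5% < FMD baseline value < 6% (at Screening Visit" (section 3.3.2). Section 6.1 sizes the trial on "group one mean and SD as 1.6 (1.16) and second group mean and SD as -0.4 (2.24"; both SDs come from one earlier trial in type II diabetes. Section 3.3.1 plans 17 per group, and section 3.4 allocates by simple randomisation.

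**The concern.** Three features of the stated analysis work against it.

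- **Baseline.** Subjects are selected on a single FMD reading within a narrow window, so regression to the mean is likely and change will then depend on the baseline value. A plain change score leaves that dependence in the error term and leaves chance imbalance between small arms uncorrected.
- **Variance.** Classical ANOVA assumes one common variance. The planning SDs differ almost two-fold, which makes that assumption doubtful. A normality check does not examine it, and Kruskal-Wallis is also sensitive to unequal spread.
- **Switching.** Whether the primary result is a comparison of means or of ranks stays open until the data are in hand.

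At stake are precision in a trial with about 14 evaluable subjects per arm and, if the spreads really differ, the error rate of the comparison with placebo. Because section 6.3 fixes these tests itself, the point is not simply detail left to an analysis plan.

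**Working it through.** **1. The plan's own sample size (section 6.1).** Difference = 1.6 − (−0.4) = 2.0. Average variance = (1.16² + 2.24²)/2 = (1.3456 + 5.0176)/2 = 3.18, so SD = 1.784 and d = 2.0/1.784 = 1.121. A two-sample t-test (noncentral t, two-sided 5%) has power 78.3% at 13 per group and 81.5% at 14. The stated 14 is reproduced, as is 3 × 14/0.8 = 52.5. The variance ratio is 5.0176/1.3456 = 3.73.

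**2. What baseline adjustment could gain.** Write week-8 FMD = a + b × baseline + e. Then change = a + (b − 1) × baseline + e, and Var(change) = (1 − b)² × s_B² + Var(e). ANCOVA removes the first term. The documents give neither s_B nor b. Assume baseline is uniform over the window 2.5 to 6: s_B = 3.5/√12 = 1.01, s_B² = 1.02. Saving = (1 − b)² × 1.02/3.18.

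| Assumed slope b | Variance removed | Saving | Power at 14 per arm |
|---|---|---|---|
| 0 | 1.02 | 32% | 93.4% |
| 0.3 | 0.50 | 16% | 87.5% |
| 0.5 | 0.26 | 8% | 84.5% |
| 1 | 0 | 0% | 81.5% |

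At b = 0.7 the saving is 3%. A chance baseline imbalance of one standard error is 1.01 × √(2/14) = 0.38 points. It shifts the unadjusted difference by (1 − b) × 0.38, that is 0.38 at b = 0, 0.19 at b = 0.5 and 0 at b = 1, against a planned difference of 2.0.

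**3. Unequal variances.** Assume placebo SD 2.24, both active arms 1.16, normal data and equal means. With 14 per arm, ANOVA pools to (1.3456 + 1.3456 + 5.0176)/3 = 2.57, so the standard error of an active-versus-placebo contrast is √(2.57 × 2/14) = 0.606. The true value is √((1.3456 + 5.0176)/14) = 0.674, so the pooled one is about 10% too small. Simulated type I error at nominal 5%:

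| Arms (active/active/placebo) | ANOVA F | Contrast on pooled error, no prior F-test | Unequal-variance (Welch) contrast |
|---|---|---|---|
| 14/14/14 | 6.1% | 8.1% | about 5% |
| 16/15/11 | 8.8% | 11.4% | about 5% |
| 14/14/23 | 3.1% | 4.2% | about 5% |

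Kruskal-Wallis gives 5.4% at 14/14/14 and 7.3% at 20/20/11. If the 51 assignments are independent draws, placebo receives 13 or fewer in about 15% of sequences, and some arm does in about 43%.

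**4. The switch itself.** With the same SDs and 14 per arm, choosing between the two omnibus tests by a normality check gave 6.6% (6,000 runs, standard error about 0.3 points) against 6.1% for ANOVA alone. No clear extra error is shown. The objection to the switch is that the target of the primary analysis is not fixed in advance.

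**The case against.** A reader might infer stronger claims than the protocol supports.

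- **That baseline FMD is ignored.** It is not; it enters by subtraction. Under randomisation the change score is unbiased, regression to the mean acts alike in all arms, and chance imbalance is ordinary random error already reflected in the standard error.
- **That the comparison with placebo runs at 8% or more.** Section 6.3 names no follow-up contrast. At 14/14/14 and the same SDs, a contrast tested only after a significant F runs at about 4.8%, and an ordinary pairwise t-test at about 5.4%. The 8% and 11% apply only to pooled-error contrasts used without that gate.
- **That the chance of a false positive on either dose is about 12%.** Two unadjusted Welch contrasts already give 7.7%, so most of that figure is multiplicity, a separate matter.
- **That the planning SDs contradict equal variance.** They come from one external trial in type II diabetes, a condition excluded here (section 3.3.3). They make equal variance doubtful and do not disprove it. If ubiquinol had no effect at all, the arms would share one distribution and ANOVA would hold its level; the inflation needs equal means with unequal spread.
- **That subjects without week 8 are dropped.** Section 6.2 says "All subjects with at least 1 FMD measurements will be part of the intention-to-treat population", but section 6.3 is silent on missing data, which is commonly settled in an analysis plan.

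The gain from adjustment also rests on assumed quantities. At slope 0 the active arm would keep a residual SD of only √(1.3456 − 1.02) = 0.57 against a planned 1.16, so the top of the range is optimistic.

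All of this stands and limits the size of the point. It does not answer why a data-chosen, unadjusted test should be preferred when the baseline is already collected and equal variance is in doubt.

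**Conclusion.** The point holds as an avoidable weakness in the stated primary analysis, not as a source of bias. The possible gain from baseline adjustment runs from 32% of residual variance down to nothing, with power at 14 per arm between 93% and 81%, depending on an unstated slope and an assumed baseline spread. The risk to the error rate is conditional on the planning SDs holding with equal means: about 6%, 9% or 3% for the F-test with arms equal, placebo smallest or placebo largest, and about 8%, 11% or 4% for ungated pooled-error contrasts. Welch stays near 5% in all three cases. The sample size does not need to rise on this account.

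**What to change.** In section 6.3, name one primary model: an ANCOVA of week-8 FMD on treatment group and baseline FMD, estimating each dose against placebo, with unequal-variance standard errors or heteroscedasticity-robust ones in a small-sample form. Delete the choice of test by normality and keep a rank-based analysis as sensitivity only. A mixed model using weeks 4 and 8 is an optional alternative, but at this size it needs more variance parameters and a stated small-sample degrees-of-freedom method.

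The cost is a wording change and one degree of freedom for the covariate. The unequal-variance method loses about one point of power against the two-group t-test behind the sample size (81.5% to 80.5% at 14 per arm). Against a three-arm pooled-error contrast the loss looks larger (87% to 80% in simulation), but that contrast runs at about 8% under the same SDs. No new data or subjects are needed.

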3.1 Study Outline

Double-blind, randomized, placebo – controlled, parallel groups clinical study with 3 intervention groups to be carried out on 51 subjects.

Three visits will be envisaged to the test facility: a Screening / Baseline / Randomization Visit and 2 Measurement Visits will be performed, each lasting approximately 1 hour. There will be 4 weeks between each visit.

At each Visits subjects should have to:

- ≥12-h overnight fast
- Avoid caffeine for 72h
- Avoid high-fat food the day before
- Avoid tobacco for at least 4-6h before
- Abstain from exercise for >12h before the test

During Screening Visit the eligibility criteria will be verified and, if fulfilled, each subject will be randomized to one of the 3 study groups after signing the Informed Consent Form.

During each visit a short physical examination will be performed and a blood sample (approximately 10 ml) will be collected from the vein in the left arm to evaluate CoQ10 levels. After acclimatisation and rest for ≥ 30 minutes blood pressure (triplicate, first discarded) and FMD (baseline or Week 4 and 8 measurement) will be measured.

At Screening Visit and at Week 4, subjects will receive the assigned test product, according to randomization, for consumption at home during the coming 4 weeks and leave the facility.

The study products include test treatment (ubiquinol, two dosages, 100 and 200 mg daily) and placebo; details on these study products are given in the study products dossiers. Each product (ubiquinol or placebo), have to be taken daily at breakfast and dinner (total two pills: 1 before breakfast and 1 before dinner).

FMD measurements will be taken as follows:

Measurement 1: baseline measurement on Day 0 (Visit 0 - Screening / Baseline / Randomization Visit)

Measurement 2: second measurement on Week 4 (Visit 1)

Measurement 3: third measurement on Week 8 (Visit 2 – End of Study Visit)

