3.3 Selection of Subjects

3.3.1 Planned number of subjects

Sample size: 51 (17 per group), healthy, adult males and females.

In females, FMD varies with the hormonal cycle. Therefore, to avoid such complications, the study will be conducted in post-menopausal female subjects only.

Subjects will be recruited from subjects referred as outpatients to U.O.C. Laboratorio Analisi – POR I.N.R.C.A. Ancona, Italy. Selection of suitable subjects will be made according to the inclusion and exclusion criteria described in the following sections.

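### The primary question is each ubiquinol dose against placebo and the sample size is for one such comparison, but section 6.3 names only a three-group omnibus test

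*Protocol*

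**What the plan says.** Three parts of the Protocol bear on the primary analysis.

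- **Question.** The primary endpoint (Synopsis and section 2) is the change in FMD "at week 8; comparison between both treatment groups and placebo". Section 3.1 describes a "parallel groups clinical study with 3 intervention groups to be carried out on 51 subjects": 200 mg daily, 100 mg daily and placebo. That makes two dose-versus-placebo comparisons.
- **Size.** Section 6.1 takes means and SDs from one earlier trial, 1.6 (SD 1.16) against -0.4 (SD 2.24), and concludes that "with 80% power and 5% two-sided significance level, 14 subjects are required for one group". It then allows for dropout ("considering a 20% dropout rate, a total of 52.5 subjects should have been enrolled") and settles on 51, which section 3.3.1 splits as 17 per group.
- **Test.** Section 6.3 lists three between-visit changes to be compared among groups (Measurement 3 vs 1, 2 vs 1 and 3 vs 2), and then says: "Parametric or non-parametric tests, ANOVA and Kruskal-Wallis tests, will be performed basing on the normality of the data".

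No dose-versus-placebo contrast, order of testing or definition of success (one dose or both) appears in the Protocol.

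**The concern.** The endpoint asks about two specific contrasts, the sample size powers one contrast, and the named test addresses a third hypothesis, that all three groups have the same mean change (or distribution). The omnibus test also responds to a difference between 200 mg and 100 mg, which is not part of the primary question. A significant result therefore does not by itself support a statement about either dose, and the 80% in section 6.1 does not describe the test in section 6.3.

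The decision rule for the only primary endpoint is thus left open. Several rules fit the text (omnibus alone, omnibus followed by pairwise tests, adjusted or unadjusted pairwise tests). They differ in error rate and power, and they could give different answers for a given dose on the same data.

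**Working it through.** **Inputs from section 6.1.** Means 1.6 and -0.4, SDs 1.16 and 2.24, two-sided 5%, 80% power, 20% dropout, 51 enrolled. **Assumptions added here:** normal data, equal arms, common SD. Kruskal-Wallis was not computed.

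**1. The Protocol's own figure.**
- Pooled SD = √[(1.16² + 2.24²)/2] = √3.1816 = 1.784. Standardised difference = 2.0/1.784 = 1.121.
- Two-sample t-test, noncentrality 1.121 × √(n/2). At n = 14 this is 2.967 on 26 df, power 81.5%. At n = 13, power is 78.3%. So 14 per group reproduces.
- 3 × 14/0.8 = 52.5 also reproduces. With 51 enrolled and 20% lost, 51 × 0.8 = 40.8 are evaluable, or 13.6 per group. The two-group power is then 80.3%.

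The calculation is correct, but for one dose against placebo.

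**2. Power of the omnibus ANOVA.** Noncentrality λ = n Σ(μᵢ − μ̄)²/3.1816, with 2 and 39 df at n = 14.

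| 200 mg / 100 mg / placebo | Σ(μᵢ − μ̄)² | λ | Power, n = 14 | Power, n = 13.6 |
|---|---|---|---|---|
| 1.6 / 1.6 / -0.4 | 2.667 | 11.73 | 84.8% | 83.6% |
| 1.6 / -0.4 / -0.4 | 2.667 | 11.73 | 84.8% | 83.6% |
| 1.6 / 0.6 / -0.4 (half effect assumed for 100 mg) | 2.000 | 8.80 | 72.6% | 71.1% |

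The value 0.6 is not in the Protocol. It stands for a graded dose response.

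**3. Power to claim a named dose with the full 2.0-point effect (n = 14).**

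| Rule | Power |
|---|---|
| Unadjusted t-test at 5% | 81.5% |
| Pairwise test after a significant omnibus, other dose full or no effect | 78% |
| Same, other dose at half effect (assumed) | 72% |
| Dunnett | 74.7% |
| Bonferroni (2.5% each) | 71.9% |

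Power to claim both doses when both have the full effect is about 71-72% with unadjusted, omnibus-gated or fixed-sequence tests, and 58% with Bonferroni.

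**4. Family-wise error (simulation, n = 14).**

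| Rule | Chance of a false claim |
|---|---|
| Omnibus ANOVA, all groups equal | 5.0% |
| Omnibus gate then unadjusted pairwise tests, any dose claim, all groups equal | 4.2-4.3% |
| Same, null dose claimed when the other dose works | 4.9% |
| Two ungated, unadjusted 5% tests sharing the placebo arm | about 9.0% |

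**5. How often the omnibus test rejects with neither dose differing from placebo at 5%.** If one dose has the full effect and the other none: 5-6% of trials. If the doses move in opposite directions by 1 point from placebo (an illustration only): the omnibus rejects in 73% of trials, and in 18-20% of all trials it does so with neither dose differing from placebo.

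**The case against.** The strongest reply has three parts.

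First, the stated test is sound as a test. ANOVA on three groups holds 5%. The conventional sequel, pairwise tests only after a significant omnibus, is a closed procedure with three groups and also stays within 5%. This stands. A reader might infer from the missing adjustment that the trial's error rate nearly doubles. The Protocol does not support that: the 9% needs ungated, unadjusted pairwise tests, and no section says these will be used.

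Second, omnibus power is not below 80% on the Protocol's own inputs. Section 6.1 gives only 1.6 and -0.4, and with those values power is about 84-85%. This also stands. A reader might infer that the trial is underpowered at 71-73%, but that rests on an assumed half effect for 100 mg.

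Third, post-hoc contrasts and multiplicity rules are often left to an analysis plan, which is not shown here. This stands for the missing detail, so that silence is not counted as a fault. It does not remove the mismatch. Section 6.3 does name a test, tied to the primary and secondary endpoints, and it is neither the comparison in the endpoint nor the one sized in 6.1. An analysis plan could add contrasts, but these Protocol sections would still disagree.

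**Conclusion.** The mismatch is real: the endpoint is dose against placebo, the sample size is for one such comparison, and the named test is a three-group omnibus that cannot say which dose, if either, works.

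Its numerical cost is moderate. The 81.5% planned for a single dose becomes about 78% after an omnibus gate and 72-75% under Bonferroni or Dunnett at 14 per group. Power to claim both doses is only about 71-72% even without adjustment. The larger error and power failures are conditional on choices or effects that the Protocol does not state. All figures rest on the section 6.1 inputs, normality, equal arms and a common SD. Simple randomization (section 3.4) does not guarantee equal arms. With SDs of 1.16, 1.16 and 2.24 and both doses at full effect, omnibus power is about 86%, so unequal variance does not change the picture in that case.

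**What to change.** In section 6.3, name the two dose-versus-placebo contrasts of week-8 change in FMD as the primary analysis, with one pre-specified rule that holds family-wise error at 5%. Say whether success means one dose or both. Report both estimates with 95% confidence intervals, and make the omnibus test and the Measurement 3 vs 2 comparison supportive. In section 6.1, state which comparison the 80% refers to.

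Several rules are valid, and the Protocol does not rank the doses, so the choice is the sponsor's:

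- **Fixed sequence** (200 mg vs placebo at two-sided 5%, then 100 mg vs placebo at 5% only if the first is significant). The first test keeps 80.3% power at 13.6 evaluable per group and 81.5% at 14. No extra subjects are needed. The price is that 100 mg cannot be confirmed if 200 mg misses.
- **Dunnett or Bonferroni.** Either dose can be claimed on its own. Section 6.1 should then give per-dose power as about 75% or 72% at 14 evaluable per group. Restoring 80% per dose needs 16 evaluable per group with Dunnett (16/0.8 = 20, so 60 enrolled) or 17 with Bonferroni (17/0.8 = 21.25, so 22 per group and 66 enrolled).

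The wording is a few sentences and should be settled before unblinding.
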